## STATISTICS

### Description of Statistical Methods

As this is a feasibility study, the analyses of the data collected will be mainly descriptive, and any statistical comparisons made will be exploratory. Continuous data will be summarized as mean (standard deviation) or median (interquartile range), if data will be skewed, and categorical data will be expressed as number and/or percentage. We will calculate the summary scores for SF36, GAD-7 and PHQ-9, as well as the score of each domain assessed by these instruments. The change in the scores (3-month follow-up minus the baseline) will be computed and as a measure to evaluate the psychological impact of the screening. We will use mixed logistic regression model to explore the genotype-phenotype relationship in the family-based data and identify candidate genetic variants associated with NS-TADs. Exploratory comparison of the outcomes (e.g. aortic diameter, distensibility and pulse wave velocity) between mutation carriers and non-carriers may be conducted. Where appropriate, we will take into account of the family structure in the statistical analyses.

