### Number of Trial Participants

Recruitment will be primarily targeted at 16 probands (index patients) affected by NSTAD, of which n=8 affected by sporadic forms and n=8 from familial forms. The first degree relatives and second degree relatives of these probands will be identified and invited to participate in the study. In our pilot study, based on the data available in a recent systematic review and the fact that we will enrol first degree relatives as well as second degree relatives, we have calculated that an average of 6 to 8 relatives for proband will be recruited, giving a total number of 128 participants to be approached ("enrollable"), and 90 to be effectively screened.

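### The 3-month change in SF36, GAD-7 and PHQ-9, with no comparison, cannot by itself measure the psychological impact of screening

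*SAP*

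**What the plan says.** All of this stands in the SAP, under Description of Statistical Methods unless another section is named.

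- Scoring: "We will calculate the summary scores for SF36, GAD-7 and PHQ-9", together with the domain scores. Continuous data in general are to be summarised by mean and SD, or by median and interquartile range if skewed.
- The derived quantity: "The change in the scores (3-month follow-up minus the baseline) will be computed".
- Its meaning: the change serves "as a measure to evaluate the psychological impact of the screening".
- Status: "the analyses of the data collected will be mainly descriptive, and any statistical comparisons made will be exploratory".
- The only group contrast named is an exploratory one "between mutation carriers and non-carriers may be conducted". It is optional, and its examples are all aortic measures.
- Under Number of Trial Participants: "Recruitment will be primarily targeted at 16 probands (index patients) affected by NSTAD", and "The first degree relatives and second degree relatives of these probands will be identified and invited to participate in the study". The section expects 128 people to be approached and 90 screened.
- Under The Level of Statistical Significance: outside the genome-wide analysis, p<0.05 is read as a potential signal, without adjustment for multiplicity.

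**The concern.** The SAP gives a before-after difference a causal name. A mean change over 3 months in people who have been screened contains whatever screening did, plus everything else that moves the scores in that time: the course of distress already present at baseline, regression to the mean, and outside events. Nothing in the SAP's definition of the measure takes these apart. The carrier contrast would not do so even if it were extended to the questionnaires, because it compares people by genotype and not by whether they were screened.

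What is at stake is the sentence the study may write about psychological impact. A fall in anxiety scores could be reported as reassurance from screening, or a flat mean as absence of harm, when the data are equally compatible with other explanations. More participants would not help: this is bias, and a larger sample only makes a biased estimate more precise.

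**Working it through.** **The plan's own figures.** The SAP gives no SD, target difference or power for the questionnaire scores, so the only figures to reproduce are the sample sizes.

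- Approached: 16 × 8 relatives = 128, or 16 × (1 proband + 7 relatives) = 128. Both fit the statement that "an average of 6 to 8 relatives for proband will be recruited".
- Screened: 90/128 = 70.3%. An uptake of 70% gives 128 × 0.70 = 89.6, which rounds to 90. The 70% is inferred; the SAP does not state it.

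**What the change estimates.** Let *s* be the effect of screening and *d* the change that would have happened without it. The expected observed change is *s* + *d*. The SAP offers nothing that estimates *d*, so *s* cannot be recovered.

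**Illustration of one possible *d*.** Suppose baseline GAD-7 (higher is worse) is raised by worry that settles by 3 months, and screening has no effect.

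Inputs:
- n = 90, from the SAP, assuming that everyone screened completes both questionnaires.
- 16 families, from the SAP, so an average of 90/16 = 5.625 people per family.
- SD of the change: 3, 4 or 5 points (assumed).
- Intraclass correlation (ICC) of the change within families: 0 or 0.1 (assumed).
- Fade: 1 or 2 points (assumed).
- Two-sided 5% level, from the SAP; a test of the change is assumed, since none is specified.

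Formulas:
- Design effect = 1 + (5.625 − 1) × ICC, which is 1 for ICC 0 and 1.4625 for ICC 0.1.
- SE = SD × √(design effect / 90).
- Chance of a significant fall = Φ(fade/SE − 1.96).

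Example: SD 4, ICC 0 gives SE = 4/√90 = 0.422; 1/0.422 = 2.37; Φ(2.37 − 1.96) = 0.66.

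| SD of change | ICC | SE | 1-point fade | 2-point fade |
|---|---|---|---|---|
| 3 | 0 | 0.316 | 0.885 | 1.000 |
| 3 | 0.1 | 0.382 | 0.744 | 0.999 |
| 4 | 0 | 0.422 | 0.660 | 0.997 |
| 4 | 0.1 | 0.510 | 0.500 | 0.975 |
| 5 | 0 | 0.527 | 0.475 | 0.967 |
| 5 | 0.1 | 0.637 | 0.348 | 0.881 |

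With no fade the chance is 0.025 in every row. A 1-point fade therefore gives about 0.35 to 0.89, and a 2-point fade about 0.88 to 1.00.

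The same sum works the other way. A true harm of +1 point with a fade of −1 point gives an expected change of 0, and the harm is not seen. That case sets the fade equal to the harm by construction; it shows what is possible, not what is likely.

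**The case against.** Several points can be made for the plan, and some of them stand.

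- **The study is exploratory.** It is a feasibility study with mainly descriptive analysis; no test of the change and no decision rule are specified, and p<0.05 is only a potential signal. This lowers the consequence. It does not alter what a before-after difference can identify, and the SAP itself assigns the interpretation.
- **The levels are not ignored.** The instruments are scored and continuous data summarised, so 3-month levels may well be tabulated. This stands: one cannot say that the plan gives the 3-month level no role. Only the change, however, is named as the measure of impact.
- **The protocol may say more.** A comparator or the timing of baseline may be set out there. The SAP names no unscreened group, but that is silence and not proof that none exists. Of those approached, 128 − 90 = 38 would not be screened, and whether they complete questionnaires is not stated. The point here is narrower: the measure, as the SAP defines it, uses no comparison.
- **The direction is open.** A reader might infer that relatives have just learned of their risk at baseline, that their distress is therefore raised, and that the bias must be reassuring. The SAP does not support this. It does not place baseline relative to invitation, the proband's diagnosis or the result. Relatives are invited before they take part, which makes invitation worry plausible. But 8 of the 16 probands have familial disease, and their relatives may have known of it for a long time. If calmer relatives are the ones who accept, or outside events intervene, the change could lean toward harm.
- **More tables do not create a control.** Counts above a cut-off at two time points are still uncontrolled. This stands too, so the added tables must be presented as description.

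**Conclusion.** The point holds as one of attribution. The SAP names a change without a comparison as the measure of what screening does to psychological health, and the change as defined does not have that property. This conclusion rests on the SAP's wording alone and needs none of the assumed values.

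The size is unknown. The probabilities of about 0.35 to 0.89 for a 1-point fade show only that a modest drift could produce a signal at this sample size. They depend on the assumed SD, family correlation and fade, and on complete follow-up of 90 people. They are not an estimate of the bias, and they presuppose a direction that the SAP does not establish. Nor does the SAP say that the result would be used to justify a larger screening programme, so that consequence should not be claimed.

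In an exploratory feasibility study this is a limited fault, but it should be corrected because it decides what the study may conclude on psychological impact.

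**What to change.** In the SAP, Description of Statistical Methods, replace "as a measure to evaluate the psychological impact of the screening" with: *to describe change from before to 3 months after screening; the change alone will not be attributed to screening.*

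Alongside the change, add two descriptive displays:

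1. Levels at baseline and at 3 months for each instrument, including norm-based SF36 scores and the numbers above a GAD-7 and a PHQ-9 cut-off. Name the norms and cut-offs in the SAP before analysis.
2. The change by screening result or carrier status, allowing for family clustering. This shows whether change differs with what people were told; it does not supply an unscreened comparison.

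It would also help to state when baseline is taken relative to invitation and result, or to cross-refer to the protocol if it is given there.

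No new participants, visits or questionnaires are needed. The cost is a change of wording, slightly more analysis of data already collected, and a weaker claim. To claim an effect of screening itself, an unscreened or delayed-screening comparison would be needed, which goes beyond this amendment.

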### Number of Trial Participants

Recruitment will be primarily targeted at 16 probands (index patients) affected by NSTAD, of which n=8 affected by sporadic forms and n=8 from familial forms. The first degree relatives and second degree relatives of these probands will be identified and invited to participate in the study. In our pilot study, based on the data available in a recent systematic review and the fact that we will enrol first degree relatives as well as second degree relatives, we have calculated that an average of 6 to 8 relatives for proband will be recruited, giving a total number of 128 participants to be approached ("enrollable"), and 90 to be effectively screened.

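### Does the SAP need to build the 8 sporadic / 8 familial quota, and the degree of relationship, into its planned analyses?

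*SAP*

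**What the plan says.** The section Number of Trial Participants sets the sample: "Recruitment will be primarily targeted at 16 probands (index patients) affected by NSTAD", "of which n=8 affected by sporadic forms and n=8 from familial forms". On relatives it says: "The first degree relatives and second degree relatives of these probands will be identified and invited to participate in the study". One average covers both forms and both degrees: "an average of 6 to 8 relatives for proband will be recruited". The projected totals are 128 people approached and 90 screened.

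The section Description of Statistical Methods says that "the analyses of the data collected will be mainly descriptive" and that "categorical data will be expressed as number and/or percentage". For the genetics: "We will use mixed logistic regression model to explore the genotype-phenotype relationship in the family-based data". The only comparison groups named are mutation carriers and non-carriers, and that comparison is optional. A closing sentence says that family structure will be allowed for where appropriate, without naming a method.

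Neither that section nor The Level of Statistical Significance mentions sporadic or familial form, or first or second degree, as a stratum, covariate or reporting group.

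**The concern.** The equal split is a quota set by the study, not the mix in which patients present. Familial probands have other affected relatives by definition and sporadic probands do not, so the share of relatives found affected should differ by form. Degree of relationship acts in the same way: for a dominant variant, a first-degree relative of a carrier has a prior carriage probability of 50% and a second-degree relative 25%.

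If the results were given only as overall percentages, each would be an average weighted by the quota and by whichever relatives came forward. A later study or screening service with a different mix could not use it directly, and informing such planning is a main purpose of a feasibility study. Form might also appear to confound the genotype-phenotype model, since familial families carry more disease and plausibly more variants.

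**Working it through.** **The plan's own figures.** Inputs from Number of Trial Participants: 16 probands, 6 to 8 relatives each, 128 approached, 90 screened.

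- Relatives only, top of the range: 16 × 8 = 128.
- Probands included, middle of the range: 16 + 16 × 7 = 128.
- Implied uptake: 90/128 = 70.3%.

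The 128 is reproduced by either route. Neither uses the split by form or degree, so no stated number depends on this point.

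**Dependence on the mix, by form.** Overall rate = w × familial rate + (1 − w) × sporadic rate, where w is the familial share. The SAP gives no rates by form, so those below are assumptions.

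| Sporadic / familial rate (assumed) | w = 0.2 | w = 0.5 (quota) | w = 0.8 |
|---|---|---|---|
| 5% / 30% | 10.0% | 17.5% | 25.0% |
| 10% / 20% | 12.0% | 15.0% | 18.0% |
| 10% / 10% | 10.0% | 10.0% | 10.0% |

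For example, 0.5 × 0.30 + 0.5 × 0.05 = 0.175. Against a population that is 20% familial, the quota-based figure is too high (17.5/10.0 = 1.75 times). Against one that is 80% familial it is too low (17.5/25.0 = 0.70 times). With equal rates there is no distortion. Neither direction nor size can be fixed from the document.

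**Dependence on the mix, by degree.** With carriage of 50% and 25%, and first-degree relatives making up 30%, 50% or 70% of the sample, overall carriage is 32.5%, 37.5% or 42.5% (for example, 0.3 × 0.50 + 0.7 × 0.25 = 0.325). These figures assume a dominant variant carried by the proband.

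**What separate reporting can deliver.** Wilson 95% limits are [p + z²/2n ± z√(p(1 − p)/n + z²/4n²)] / (1 + z²/n), with z = 1.96. The even split of the 90 screened is an assumption.

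- Observed 20%, n = 90: 13.0% to 29.4%.
- Observed 20%, n = 45 (one form): 10.9% to 33.8%.
- Observed 70% uptake, n = 128: 61.6% to 77.3%; n = 64: 57.9% to 79.8%.

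These ignore clustering within 16 families, so the true intervals are wider. Form crossed with degree would leave 90/4, about 22 people per cell, drawn from 8 families per form. Such tables describe the sample usefully but support little inference.

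**Form as a model term.** Familial form means that relatives have disease. In a model with disease as the outcome and genotype as the exposure, form is partly defined by the outcome and may itself result from a shared variant. Adjusting for it could condition on the outcome and absorb the genetic signal under study. If sporadic families contain few or no affected relatives, the form term may also come close to separation.

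**Reweighting.** Weighting to the clinic's case mix needs the share of familial cases in the clinic. A fixed quota cannot supply it, and the SAP does not mention such data.

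**The case for a change.** The best argument for a change is that reporting groups and model terms belong in the statistical section. The SAP creates a stratum and then does not mention it again. The forms differ by definition, so only the size of the difference has to be assumed. The family-structure sentence, read generously, deals with correlation among relatives; it neither promises rates by form or degree nor adjusts for form. The remedy would be cheap: form must be known to fill the quota and degree to identify the relatives, so only wording and table columns are needed.

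Much of this stands. The SAP is silent on form, and its family-structure wording is only a partial answer on degree. A breakdown by form, with any overall rate described as specific to this sample, is good reporting. But silence is not an instruction to pool. Uptake, yield and carrier rate are not named as estimates in this document, and their definitions may sit in the protocol, which is not shown. The case for action therefore comes down to writing out a tabulation that the quota itself already invites.

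**Conclusion.** No change is needed. The observation is accurate as far as it goes: the quota is fixed by design, both degrees of relative are enrolled, and neither appears by name in the analysis. An overall percentage would be specific to this mix if the groups differ.

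It remains a gap that analysts fill sensibly. The study calls itself a feasibility study with mainly descriptive analysis, and an equal quota is a fair way to make sure that both forms are represented and can be described. Followed as written, the plan gives a sound description of its own sample, and the 16, 128 and 90 stand.

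The changes that would alter an analysis do not earn their place: a fixed effect for form is a trade-off that may remove genetic signal, and reweighting lacks its input. The illustrated shifts (17.5% against 10.0% or 25.0%; 15.0% against 12.0% or 18.0%; none with equal rates) rest entirely on assumed yields and case mixes. The conclusion assumes that form and degree are recorded for every family, as the recruitment scheme requires, and that the report shows results by form. It would be different if the SAP said that results would be given only for the whole sample.

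### Do the planned numbers (6 to 8 relatives per proband, 128 approached, 90 screened) contradict each other?

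*SAP*

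**What the plan says.** The point concerns one paragraph of the SAP, section Number of Trial Participants. It sets the main target: "Recruitment will be primarily targeted at 16 probands (index patients) affected by NSTAD", split into 8 sporadic and 8 familial cases. First- and second-degree relatives of these probands are then invited. Citing a systematic review, the paragraph expects that "an average of 6 to 8 relatives for proband will be recruited, giving a total number of 128 participants to be approached", a total which it also labels as the enrollable group. The sentence ends with the last stage: "and 90 to be effectively screened".

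The SAP gives no uptake rate linking 128 to 90. It does not say whether either total counts the 16 probands.

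**The concern.** Three features of the sentence invite suspicion.

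- The verb says that 6 to 8 relatives per proband are recruited, which with 16 probands means at least 96 relatives. Only 90 people reach screening, fewer than that minimum.
- A range goes in and a single total comes out, with nothing to show which point of the range was used.
- The total is described as participants, yet it equals the upper end of the range multiplied by 16, with no room for the probands themselves.

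If this were a real contradiction, the expected yield of a feasibility study would be undefined. Suppose 75 relatives were screened. That would match the plan if the 90 includes the 16 probands (90 - 16 = 74 relatives), but would fall 17% short if all 90 are relatives (1 - 75/90 = 0.167). The size of the exploratory carrier comparisons would be equally uncertain.

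**Working it through.** **Inputs**, all from SAP section Number of Trial Participants: 16 probands; 6 to 8 relatives per proband; 128 approached; 90 screened. No uptake rate is given.

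**Step 1: reproduce 128.**

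| Relatives per proband | Relatives only (16 x k) | With probands (16 x k + 16) |
|---|---|---|
| 6 | 96 | 112 |
| 7 | 112 | **128** |
| 8 | **128** | 144 |

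The stated figure is reached exactly in two ways. Reading A uses the upper end of the range and counts relatives only. Reading B uses the midpoint and adds the probands, which suits the label participants. Either is a legitimate way to turn an average of 6 to 8 into one planning number.

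**Step 2: relate 90 to 128.** The implied uptake is 90/128 = 70.3%. Conversely, 0.70 x 128 = 89.6, which rounds to 90. The two totals are labelled as different stages, so the second should be smaller than the first.

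**Step 3: test the literal reading of the verb.** Relatives screened per proband:

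- if the 90 are all relatives, 90/16 = 5.6;
- if the 90 include the 16 probands, 74/16 = 4.6.

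Both are below 6. So 6 to 8 cannot be the number screened. Nor can it be the number who agree out of those approached, unless everyone agrees, because the sentence derives the approached total from it. The only reading under which the sentence works is that 6 to 8 relatives per proband are identified and approached.

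**Step 4: how much the remaining ambiguity is worth.** Under Reading A uptake among relatives is 90/128 = 70.3%. Under Reading B, if all 16 probands are screened, it is (90 - 16)/(128 - 16) = 74/112 = 66.1%. The gap is 4.2 percentage points. For comparison, the simple binomial standard error of the Reading A proportion is sqrt(0.703 x 0.297/128) = 0.040, or 4.0 points, before any allowance for clustering within families. The two readings differ by about one standard error of the quantity the study would observe.

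**Step 5: look for a use of 128 or 90 elsewhere.** Description of Statistical Methods calls the analyses mainly descriptive and any comparisons exploratory. The Level of Statistical Significance sets a 10% false discovery rate for the genome-wide analysis and a 0.05 signal level for the rest. Neither section uses 128 or 90, and the SAP has no power calculation, precision target or progression threshold.

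**The case for a change.** The best argument for requiring a correction is that this sentence is the SAP's only projection of how many people will be screened, in a study whose purpose is feasibility. A planning figure with two exact but incompatible derivations leaves room to choose the flattering one once the data are in. Rewording costs nothing and needs no extra patients.

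Part of this stands. The verb is wrong for the stage it describes, the composition of 128 and 90 is not stated, and the uptake has to be inferred. Saying that recruited must mean approached concedes that the text is loose.

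The rest does not carry. The comparison of 90 with a minimum of 96 sets people screened against people said to be recruited, and the SAP does not equate those stages. The choice after the fact needs a success criterion to be applied to, and the SAP states none. Any such rule in the protocol would have to define its own denominator. The target that actually governs recruitment, 16 probands in two groups of 8, is unambiguous.

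Replacing the sentence with a fixed range would also overreach. At 70.3% uptake, 96 to 128 relatives gives 67.5 to 90 screened, but only if Reading A is what the sponsor meant. Under Reading B the corresponding range is 112 x 0.703 = 79 to 144 x 0.703 = 101 people including probands, and 90 is then mid-range, not the best case. The SAP does not settle which was intended.

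**Conclusion.** No change is needed. Neither 128 nor 90 is shown to be wrong: 128 follows exactly from the stated inputs, and 90 follows from 128 at an uptake of about 70%. What survives is a clerical slip in one verb and two missing details, the assumed uptake and whether probands are counted. Those details move the relatives screened per proband between 4.6 and 5.6, and the implied uptake among relatives between 66% and 70%.

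An analyst following the SAP would tabulate probands and relatives separately at each stage (identified, approached, screened), and that table removes the ambiguity whichever reading was meant. No endpoint, test, threshold or descriptive summary would differ.

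This rests on two assumptions: that the verb is read as approached, the only sense under which the sentence coheres; and that no decision rule outside the SAP depends on 128 or 90. Only the SAP was available for this check. If the sponsor is revising the section for another reason, a word on who is counted would be welcome, but the point does not justify an amendment by itself.
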